**Data Collection Strategy** 

Data Collection Process/Schedule: Fourteen trained peer mentors will deliver the intervention in each wave and one full-time study coordinator (SC) will conduct screening, consent, enrollment procedures, and support group moderation. The primary method of data collection will be face to face interview. Mentees will be assessed at baseline, mid-intervention (3 months from baseline), immediately post-intervention (6 months from baseline), and 6 months post-intervention (12 months from baseline). Physical examination and laboratory evaluation will be achieved by in-person clinic visit when recent SLEDAI scores are not available in the database record of a given participant. Social support control participants will complete assessments on the same schedule as mentored participants. Given evidence that peer support may be just as beneficial to the supporters as it is to the person being supported, [118,119] mentors will be assessed on the same schedule as mentored and control participants, using the same tools.

## Primary Outcomes for Aim 1 will include:

Quality of Life: The LUP-QOL incorporates the Medical Outcomes Study (MOS) Short Form 36 Health Survey (SF-36) and the Functional Assessment of Chronic Illness Therapy-Fatigue (FACIT-F), which are reliable and valid instruments that are frequently used in quality of life studies of persons with lupus.[120,121] Self-Management: The Patient Activation Measure (PAM)[122,123] assesses an individual's knowledge, skill, and confidence for managing their health and healthcare. Individuals who measure high on this assessment typically understand the importance of taking a pro-active role in managing their health and have the skills and confidence to do so.

### Secondary Outcomes for Aim 1 will include:

Treatment Credibility: To assess for differences in outcome expectancy, a modified treatment credibility scale developed by Borkovec and Nau (1972) will be used. Four of the questions will be used for this study, with 10-point Likert scales. These include questions regarding how logical the treatment seems, how confident participants are about treatment, and their expectancy of success. Satisfaction with Care: Satisfaction with Care will be measured with a previously validated general scale to measure satisfaction/dissatisfaction with health care. The 2-item scale ranges from 1 (Strongly Agree) to 5 (Strongly Disagree).

## Covariates for all three aims will include:

Demographics: Previously validated items from the 2002 National Health Interview Survey [NCHS 2004] will be used to capture age, marital status, education, household income, and health insurance. The 28item Brief Index of Lupus Damage (BILD) was developed as a patient-reported measurement of lupus disease damage designed to quantify cumulative organ damage due to SLE regardless of attribution. The self-administered version of the BILD has been validated in a predominantly African American independent community-based cohort of SLE patients from the Southeastern US.[67] Coping: Coping will be assessed by the Arthritis Self-Efficacy Scale pain and other symptoms sub-scale,[124] which consists of 11 items designed to measure confidence in one's ability to manage the pain, fatigue, frustration, and other aspects of disease.[64] Depression: The PHQ-9 is a brief questionnaire that scores each of the 9 DSM-IV criteria for depression as "0" (not at all) to "3" (nearly every day). PHQ-9 score > or =10 have a sensitivity of 88% and a specificity of 88% for major depression.[125] We will use a modified version of the PHQ-9 that does not include the last question about suicidality, making it the PHQ-8. Anxiety: General Anxiety Disorder (GAD) will be assessed using the 8-item anxiety scale (GAD-8). This is a valid and efficient tool for screening for GAD and assessing its severity in clinical practice and research.[126] Perceived Stress: The perceived stress scale (PSS) is a 4-item scale that assesses the degree to which the respondent finds situations stressful.[127] Responses range from "0" (never) to "4" (very often) and questions ask about the frequency of feelings related to events in the previous month. The Cronbach alpha value is 0.69 and scores are highly correlated with stress, depression and anxiety. Chew Health Literacy Screening: The Chew Health Literacy Screening Survey[128] is a 3-item instrument designed to rapidly screen patients for potential health literacy problems. To test whether unique needs are better met in the group receiving the peer mentorship intervention compared to the group receiving social support, this instrument will be adapted to include questions about understanding the medical regimen, including considerations around depression, medication concerns (possible side effects and interactions), and physical symptoms (pain and fatigue), and knowing which symptoms should trigger a doctor visit.[35,37,77] Measures of Social Support, Trust, and Patient Centered Care will be administered to test

whether unmet needs around trust in the provider, communication with providers, receiving adequate information from medical staff about treatment side effects, and having access to telephone support and advisory services are better met in the group receiving the peer mentorship intervention compared to the group receiving social support. Social Support: The Medical Outcomes Study (MOS) Social Support Survey[129] will be used to measure social support. The total scale (d=0.97) and subscales (d=0.91 to 0.96) have high internal consistency, good criterion and discriminant validity, and one-year test-retest reliability (0.72 to 0.76). Trust: Trust will be measured using The 17-item Multidimensional Trust in Health Care Systems Scale (MTHCSS).[130] Items are scored on a 5-point Likert scale with scores ranging from 5 (strongly agree) to 1 (strongly disagree). The higher scores represent greater trust in the healthcare systems. Patient Centered Care: Patient-Centered Care will be measured using the Modified Picker Survey. It is a 7-item scale that measures patients' experience with the physician. Scores range from 1 (Always) to 4 (Never).

Methods for AIM 2: Determine the impact of a peer mentorship intervention in African American women with SLE on clinical indicators of disease activity and clinical profile that indicates success of the intervention

Disease activity will be assessed using both physician assessment and patient-reported outcome measure. The Systemic Lupus Activity Questionnaire (SLAQ)[131] asks a single Patient Global Assessment (PGA) question about presence and severity of lupus activity over the past month, questions on 24 specific symptoms of disease activity and a single Numerical Rating Scale (NRS) asking the patient to rate disease activity on a scale of 0-10 over the past three months. Use of immunomodulatory drugs and prednisone (total dose and tapers) will also be assessed. For physician assessment of disease activity, the Systemic Lupus Erythematosus Disease Activity Index (SLEDAI) has been individually validated and found reliable in clinical trials. SLEDAI scores are routinely collected as part of regular visits and clinical, demographic, genetic, disease activity/damage, genetic, and laboratory data are stored in the longitudinal web-based SLE database at MUSC as part of NIH-funded P60 and P30 grants (see [name] biosketch). All clinicians recording SLEDAI scores are trained in this assessment with annual refresher courses as part of their participation in industry-sponsored clinical trials. SLEDAI scores for each participant will be extracted from the database when available for dates within the same month as baseline, mid-intervention, and post-intervention data collection points. When scores are not available in the database, the participant will be scheduled for a clinic visit that will include vitals, blood collection, and labs to ascertain SLEDAI score. Clinic visits will take place within the South Carolina Clinical & Translational Research Institute (SCTR) Research Center (Research Nexus) at MUSC. The SC will coordinate questionnaire administration, clinic visits for SLEDAI ascertainment, and data entry. Physical examination and laboratory evaluation will be achieved by in-person clinic visit when recent SLEDAI scores are not available in the database record of a given participant. Social support control participants and mentors will complete assessments on the same schedule as mentored participants. The SLEDAI is a multicomponent, 24 question survey of clinical and laboratory signs and symptosm used as a representation of a physician's assessment of a patient's disease activity over the last 30 days (see Appendix). Items are weighted based on their severity ranging from a multiplier of 8 to no multiplier (i.e. 1). The maximum 'score' for the test is 105.[132] Validated clinically meaningful changes in SLEDAI scores are -6 for improvements and +8 for worsening disease activity.[133]

Methods for AIM 3: Determine the cost and cost-effectiveness of a peer mentorship intervention on disease self-management, disease activity, and HRQOL, in African American women with SLE Resource use and cost information will be collected to inform a well-designed economic study of the cost-effectiveness of the use of peer mentors for SLE patients in the acute care setting. Cost of the intervention will include all personnel, equipment, supply and space cost associated with training and use of peer mentors, in real time dollar values. MUSC inpatient and outpatient costs of healthcare utilization of any MUSC services will be collected from MUSC administrative billing data based on ICD9/10 codes, Medicare Diagnosis Related Group (MSDRG), and CPT codes related to lupus to estimate distributions of cost for the medical care resources used. Resource use and cost data will be accessed through the Services, Pricing, and Application for Research System (SPARC Requests), which is available to MUSC-based investigators under MUSC's Clinical and Translational Science Award (CTSA). The system allows for easy access to pricing for services across the MUSC campus and its providers and focuses on billing compliance and budgetary analysis. In order to extract data from the MUSC record systems, services are

requested through an online portal and data is then provided through direct consultation. Within the SPARC system, members of the study team will also be able to track service utilization and pricing throughout the duration of the study. Questionnaire responses will be used to ascertain care resources that patients use during the study period from other hospitals or entities who are not part of the MUSC record system.

Healthcare Utilization: Stanford Patient Education Research Center Questionnaires[134,135] assessing medical outcomes such as hospital visits will be adapted to include questions related to use of other services, such as ER visits, other medical care resources of importance to patients, economic and financial barriers to use of care outside the hospital setting including loss of time at work/productivity, and any issues related to recidivism of patients once they no longer have mentor support.[136-138]

Power and Sample Size Justification: The sample size calculation and power analyses are based on the primary outcome of change in HRQOL between baseline and 12 months post intervention. The minimum sample size was based on detecting a clinically meaningful difference of 0.35 standard deviation units (medium effect) based on prior studies.[87,93,139-143] Essentially, this is equivalent to testing the interaction between time and group. Assuming 3 measurement time points, level of significance p=0.05, two-tailed comparison, correlation between pairs of measurements within participants (interclass correlation) no larger than p=0.6, compound symmetry covariance structure, we estimate that 123 participants per group (total n=246) are needed to detect, with 80% power, a standardized effect size of at least 0.35sd. This sample size includes a 20% inflation for attrition at 12 months. This effect size is robust enough to provide sufficient power for the outcomes listed under aims 1 and 2 and is consistent with data from our pilot study of 20 mentees and 7 mentors (see preliminary data). The pre-post differences in the outcomes (such as overall social support, positive social interaction, tangible support, vitality, emotional support, social functioning, general health, coping, etc), ranged from 0.35 to 0.88 standard deviation units. Although these calculations account for within patient clustering through the intera-class correlation mentioned above, clustering within mentors and mentees are assumed to have minimal intra-class correlation based on pilot data, especially since the cluster sizes would be at most 3 at a given wave. However, a multi-level model will be used in the analysis to verify this. Since the effect size planned is conservative, if the clustering leads to higher intra-class correlation, we would still be able to detect meaningful differences. We will also consider including mentor as a fixed effect in the model.

Randomization Procedure: Participants recruited for the mentored or control (support group) portion of the study will be randomized using a block randomization procedure to assure equal sample sizes in the mentored and control groups. Using a block size of 3, participants will be assigned to the appropriate treatment condition as they enroll in the study until the block is completed. Then the following 3 participants will be assigned based on the next block.[144] Once a patient is randomized and attends the first session, she will be entered into the study and included in the intent-to-treat analysis plan. Subjects will remain blinded to group allocation until after the completion of baseline assessment. The only members of the research team who will be aware of randomization assignment will be the Research Coordinator, and the statistical analyst in charge of randomization. Randomization will occur at the patient level. As such, we will take the following steps to minimize contamination between the two arms of the study: 1) patients in the intervention and control arms will be instructed not to share intervention materials with family members, friends, or other clinic patients; 2) patients will be given instructions not to disclose their treatment assignment to their assessment interviewers.

Data Management: Data will be captured via REDCap (a free, secure, web-based application) and overseen by a data management and analysis team comprising statisticians at MUSC. Data will be collected electronically in password-encrypted files. A part-time masters-level statistician will be responsible for data management. Data will be reviewed on a bimonthly basis and issues will be communicated to the project coordinators. In particular, outlying and inconsistent data values, as well as missing data, will be the targets of the data quality review.

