# Recruitment Strategy Recruitment of Mentees

Mentees (n=300; 150 mentored, 150 support group) will be primarily recruited by a direct mailing to female African American lupus patients currently enrolled in the MUSC P30 Core Center for Clinical Research (CCCR) SLE database who have agreed to future contact as well as lupus patients from the MUSC clinics not in the registry. Flyers containing the same information contained in recruitment letters will be posted in MUSC lupus clinics and shared with local SLE support groups, other SC rheumatologists and arthritis health professionals, and local chapters of the Lupus and Arthritis Foundations for distribution to their patrons. If target recruitment is not achieved within the desired timeframe by self-selection, patients will be approached individually during clinic encounters, by phone, and/or repeated mailed/emailed or patient health record portal invitation. Patients who have indicated that they are willing to be contacted for future research in their MCRC consent forms will serve as the base for these invitations. Recruitment letters and flyers will also be shared with other academic medical institutions with eligible patient populations. Patients outside of the MUSC system who express interest will still be able to participate. They will not be required to travel to MUSC as informed consent can be obtained and questionnaires completed via REDCap, study materials can be mailed, and all other study activities can be achieved by phone.

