intervention can be compared with any changes in MUSC health services utilization costs for emergency department, inpatient and outpatient care for the intervention relative to the control group. In addition to a comparison of intervention cost with average difference between MUSC costs for intervention and control group 12 months post baseline, generalized linear cost models can be estimated to examine the association of the treatment with MUSC health services costs while adjusting for patient demographics (age, gender, race/ethnicity, co-morbidities) and clinical outcomes. MUSC does not provide cost information, only charges. In addition we will estimate the impact on work loss and income by estimating the changes in days lost to illness and income based on values provided by participants. We will use the year for which the hospital charge and income data is reported and adjust for inflation as appropriate using the US Department of Labor Consumer Price Index. Inpatient and outpatient MUSC costs will be compared separately and together between the control and intervention groups. Bootstrapping methods will be used to conduct sensitivity analyses for all cost models. Sensitivity analysis will be performed by estimating a separate MUSC health services cost model while adjusting for each clinical outcome to insure robust results regarding the marginal effect of the treatment on MUSC health services costs. Park tests will be conducted to determine the best fit for the cost data in specifying the generalized linear model. In the event of many zero values, a two-part model will be used to first examine the association of the treatment with the likelihood of any MUSC costs and then the conditional generalized linear cost model, conditional on having non zero MUSC cost value for the patient. The ICR will be reported as a single ratio with no uncertainty attached to it. Therefore, standard statistical characteristics such as confidence intervals or hypothesis test to compare it to an a priori ICR from another study are not applicable. We will calculate the ICR and a clinically relevant interpretation of the outcome will be p Human Subjects Involvement and Characteristics. The Peer Approaches to Lupus Self-Management (PALS) study is a randomized controlled trial designed to examine whether a new, culturally tailored peer mentoring intervention improves disease self-management, indicators of disease activity, and health related quality of life (HRQOL) in African American women with systemic lupus ervthematosus (SLE). African American women with active SLE will be recruited as mentees and peer mentors who are considered competent in the management of their condition will be identified and recruited to provide modeling and reinforcement to participants. We will recruit mentees for 300 observations (150 mentored and 150 support group) and up to 60 mentors. Mentees and mentors will be primarily recruited from the longitudinal web-based SLE database at the Medical University of South Carolina (MUSC) in three cohorts. As part of each cohort, mentors (n=20) will be trained to deliver intervention content, prior to being paired with up to three mentees (n=50). The peer mentoring intervention will occur by twelve 60minute telephone or video sessions carried out across the course of 24 weeks. In each cohort, social support controls (n=50) will participate in a lupus support group created for this project, on the same schedule as peer mentoring sessions. All participants (mentees, mentors, and social support controls) will be assessed using validated measures of patient reported outcomes and biological indicators of disease activity at baseline, mid-intervention (3 months from baseline), immediately post-intervention (6 months from baseline), and 6 months post-intervention (12 months from baseline). For each cohort, outcomes for mentees randomized to the mentored group will be compared with the outcomes of mentees randomized to the social support control group. A booster session will be incorporated for mentored participants at 3 months post-intervention to encourage retention.

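### Aim 3 collects care outside MUSC but models MUSC amounts only, and it sets billed charges against the resource cost of the intervention without conversion

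*Combined protocol and SAP*

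**What the plan says.** **Data.** Methods for AIM 3 states that "inpatient and outpatient costs of healthcare utilization of any MUSC services will be collected from MUSC administrative billing data", using lupus-related diagnosis and procedure codes. The same section covers care elsewhere: "Questionnaire responses will be used to ascertain care resources that patients use during the study period from other hospitals or entities" that lie outside the MUSC record system. It gives no unit prices for that care. The intervention is valued from its personnel, equipment, supply and "space cost associated with training and use of peer mentors, in real time dollar values".

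**Who can enrol.** Under Recruitment of Mentees: "Patients outside of the MUSC system who express interest will still be able to participate". Recruitment material also goes to other academic centres, although most recruitment is expected from MUSC.

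**Analysis.** In the AIM 3 part of the Overview of Statistical Analysis Plan, the cost model is fitted "to examine the association of the treatment with MUSC health services costs while adjusting for patient demographics" and clinical outcomes. If there are many zeros, "a two-part model will be used to first examine the association of the treatment with the likelihood of any MUSC costs", followed by a cost model "conditional on having non zero MUSC cost value for the patient". Inpatient and outpatient MUSC amounts are compared between arms, and the intervention cost is compared with the average between-arm difference in MUSC amounts at 12 months. The section then notes: "MUSC does not provide cost information, only charges". The only price adjustment it names is for inflation, through the Consumer Price Index.

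**Ratio.** The incremental cost-effectiveness ratio (ICR) is built from the difference in QALYs and the difference in cost. What counts as cost is not listed.

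**The concern.** There are two separate faults.

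1. **Coverage.** Outside care is collected but never priced or carried into a cost outcome. A woman with no MUSC bill may have used no care or may have been treated elsewhere, and the first stage of the two-part model treats both alike. MUSC patients who also use other hospitals are only partly counted. The stated perspective is provider, insurer and patient, and the last two also bear costs outside MUSC.
2. **Valuation.** Methods for AIM 3 speaks of MUSC costs, but the analysis section says only charges are available. The intervention is counted at resource cost. Comparing one with the other is not like for like.

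At stake is the comparison that would tell a payer whether the programme pays for itself. The planned safeguards do not address either fault. The bootstrap deals with sampling variability, the named sensitivity analysis changes the clinical covariate, and the ICR is to be reported with no uncertainty.

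**Working it through.** The documents state no incremental cost, ICR, outside share or cost-to-charge ratio, so there is no figure to reproduce. The values below are assumptions that show how the two faults act. They are not trial estimates.

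**Inputs**
- q, the share of women treated outside MUSC: not given; assumed 0 to 0.30.
- r, charges divided by cost: not given; assumed 1 to 4 (a cost-to-charge ratio of 1 down to 0.25).
- D, the true between-arm difference in mean health-care cost.
- I, the intervention cost per woman.

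**Formula.** Suppose outside women are recorded as zero, q is the same in both arms, and the effect on cost is the same for MUSC and outside women. Then

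measured difference = (1 − q) × r × D.

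| q | r = 1 | r = 2 | r = 3 | r = 4 |
|---|---|---|---|---|
| 0 | 1.0 | 2.0 | 3.0 | 4.0 |
| 0.10 | 0.9 | 1.8 | 2.7 | 3.6 |
| 0.20 | 0.8 | 1.6 | 2.4 | 3.2 |
| 0.30 | 0.7 | 1.4 | 2.1 | 2.8 |

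Entries are multiples of D. Missing outside care alone (column r = 1) attenuates by the outside share. Charges alone (row q = 0) inflate by r. The two offset exactly only when r = 1/(1 − q), which is 1.11 at q = 0.10 and 1.43 at q = 0.30.

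**Effect on the comparison with intervention cost.** Assume I = 1,500 and a true saving of 1,000 per woman, so the true net cost is 1,500 − 1,000 = +500. The measured net cost is 1,500 − (1 − q) × r × 1,000:
- q = 0.20, r = 1: 1,500 − 800 = +700
- q = 0, r = 2: 1,500 − 2,000 = −500
- q = 0.20, r = 2: 1,500 − 1,600 = −100
- q = 0.20, r = 4: 1,500 − 3,200 = −1,700

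In this example, using charges turns a net cost into an apparent saving.

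**If outside women are set to missing instead.** The factor (1 − q) for wholly outside women drops out. The result then describes MUSC patients only, and their own care at other hospitals is still left out. The factor r is unaffected.

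**The case against.** Several points on the other side stand.

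- **Zero coding is an inference.** A reader might conclude that women treated elsewhere must enter as zero cost. No section says how women without MUSC records are coded, and the two-part model is used only if zeros are numerous. What stands is that no rule separates true zeros from unobserved care.
- **The ICR is not shown to be wrong.** A reader might infer that charges and resource costs are combined in one ratio. The plan introduces the MUSC comparison as additional to the QALY and ICR outcome, and it speaks of QALYs relative to the cost of the intervention. It also mentions hospitalisation charges under perspective, so inclusion is possible but unproven.
- **The outside share may be small.** Mentees come mainly from MUSC, with a stated pool of 557 for 300 places. Randomisation should balance the share between arms on average, so the likely effect is attenuation.
- **Enrolment mix alone does not set the direction.** Suppose the outside share is 0.10 to 0.40 and the cost-to-charge ratio 0.2 to 0.6 (both assumed), so that charges are 1.67 to 5 times cost. The net multiplier then runs from 0.6 × 1.67 = 1.0 to 0.9 × 5 = 4.5, never below 1. A shrunken difference needs charges close to cost.
- **The pilot dollars do not size this.** The fall of $24,289 − $872 = $23,417 per person is an uncontrolled change in hospitalisation charges over two months before and after. Rescaling it says nothing about a 12-month difference between arms.

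None of this removes the explicit comparison of intervention cost with MUSC charges, or the absence of outside care from every health-care cost model.

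**Conclusion.** The point holds as a fault in the planned cost comparisons. Followed as written, they leave out care that the trial collects, cannot tell no care from care elsewhere, and weigh charges against resource cost with no conversion beyond inflation. The coverage fault attenuates the measured between-arm difference by roughly the outside share, if that share is balanced, effects are alike and outside women are recorded as zero. The valuation fault inflates the difference by the charge-to-cost ratio. The documents give neither quantity, so the net size cannot be stated. Whether the ICR is affected depends on cost terms that are not itemised. The change should be made, but it is not critical to the trial: the sample size rests on quality of life, not on Aim 3.

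**What to change.** Amend the AIM 3 analysis in three places.

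1. Define the main cost outcome as intervention cost plus MUSC use plus questionnaire-reported outside use, for every participant, valued with one stated set of unit prices. Use the same terms in the ICR and list them.
2. Restrict the MUSC-billing models, including the two-part model, to women whose usual care is at MUSC. In those models treat the others as unobserved, not as zero.
3. Where MUSC charges are used, convert them to costs with a stated cost-to-charge ratio. Show both the ICR and the comparison with intervention cost over a stated range of that ratio.

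The questionnaire and billing codes are already planned, so no new participant data source is needed. The work is not only rewording. The billing codes and self-reported visits carry no prices, so an external price source has to be chosen and named. Self-reported use is less exact than billing, and the MUSC-only models lose some participants.
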